Individuals with painful temporomandibular joint disease, internal irregularity and/or inflammatory joint disease with a mouth opening of less than 25 mm, pregnant and lactating individuals, individuals who do not come to their postoperative controls, individuals using different drugs other than those recommended, individuals who are allergic to the study drugs and materials to be used are unable to work. will be excluded.

It is planned as randomized, prospective, bilateral and single blind. 50 patients will be divided into two groups.

First group (study group, one side of the same patients): Leukocyte platelet-rich fibrin (L-PRF, 2700rpm,12 min); For the second group (control group, the other side of the same patient): type 1 collagen impregnated with injectable platelet-rich fibrin (I-PRF, 700rpm, 3min) will be used. Both surgical fields will be sutured with 4\0 silk sutures (18mm, 3\8 sharp, 75cm black). Which material will be used first by which side will be determined randomly. After 4 weeks, the other side will be operated. Platelet-rich fibrin (L-PRF) will be obtained by centrifugation at 2700 r.p.m. for 12 minutes and placed in the extraction socket within 2 minutes. Injectable platelet-rich fibrin (I-PRF) will be obtained by centrifugation at 700 rpm for 3 minutes, drawn into the injector, absorbed into type 1 collagen and applied into the socket within a maximum of 2 minutes.

Check-ups will be made in the first session of the patients, on the 2nd and 7th days after the operation, and in the 2nd and 4th weeks. After the operation in all patients; amoxicillin 500mg(Largopen 500mg, 3*1), ibuprofen 600mg (Brufen 600 mg, 2*1), benzydamine HcL + chlorhexidine Gluconate mouthwash (Andorex 200ml mouthwash, 3*1) will be used routinely. Sutures will be removed after 1 week. Pain in patients will be evaluated with the VAS scale (at 3, 6, 12, and 24 hours and on days 2, 3, 4, 5, 6, and 7). For the evaluation of edema, measurements between Angulus-tragus, angulus-lateral canthus, angulus-nasalis, angulus-labial commissura and angulus-pogonion points will be made just before the operation, 2 days after the operation and 7 days after the operation.

To assess trismus, mouth opening—the distance between the incisal edges of the central teeth at maximum mouth opening—will be measured immediately before, 2 days after, and 7 days after the operation.

Soft tissue opening amount (in mm), plaque index, values and periodontal measurements of the second molar tooth in the incision line will be measured before the operation, 2 days after the operation and 7 days after the operation. Other postoperative complications will also be evaluated in the control sessions. Statistical analysis will be made and interpreted for the data obtained.

Statistical Data Analysis:

Descriptive statistics for continuous variables in our study; As Average, Standard Deviation, Minimum and Maximum values; will be expressed as numbers and percentages for categorical variables. Mann-Whitney U analysis will be used to compare group means in terms of continuous independent variables. In addition, the Wicoxon test will be calculated in the comparison of double dependent groups. In order to determine the relationship between these variables, Spearman correlation coefficients will be calculated separately for the groups. Chi-square test will be used to determine the relationship between groups and categorical variables. Statistical significance level will be taken as 5% in calculations and SPSS statistical package program will be used for calculations.

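### The plan gives the comparison of group means to an unpaired test although the groups are two sides of one patient, leaves the Wilcoxon pair undefined, and states no between-material use of preoperative values or operation order

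*Combined protocol and SAP*

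**What the plan says.** **Design (Study Protocol, Methods and Procedures).** The groups are not separate patients. The L-PRF arm is "First group (study group, one side of the same patients", and the other arm, type 1 collagen with I-PRF, is the opposite side. On allocation and timing: "Which material will be used first by which side will be determined randomly. After 4 weeks, the other side will be operated".

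**Measurements (same section).**
- Facial distances, for edema: "points will be made just before the operation, 2 days after the operation and 7 days after the operation".
- Mouth opening, for trismus: the same three times. It is "the distance between the incisal edges of the central teeth at maximum mouth opening", so it belongs to the patient and not to a side.
- Soft tissue opening, plaque index and periodontal measures also have a preoperative value: "plaque index, values and periodontal measurements of the second molar tooth in the incision line will be measured before the operation".
- Pain has postoperative values only: "Pain in patients will be evaluated with the VAS scale (at 3, 6, 12, and 24 hours", then daily to day 7.

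**Analysis (Statistical Data Analysis).** Two sentences cover tests on continuous outcomes: "Mann-Whitney U analysis will be used to compare group means in terms of continuous independent variables" and "In addition, the Wicoxon test will be calculated in the comparison of double dependent groups". The section names no outcome, time point, choice of raw value or change, baseline term or order term.

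**The concern.** The two observations from a patient are correlated, so a test for independent samples does not fit the comparison of sides. Yet Mann-Whitney is the only continuous-outcome test that the text ties to group means. Whether a paired comparison of materials is planned at all depends on what the Wilcoxon pair is, and two readings are open.

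- **Reading (a), before versus after on one side.** Wilcoxon then says nothing about the difference between materials. Mann-Whitney is the only between-material test, and it ignores the pairing.
- **Reading (b), side versus side.** The comparison is paired and valid, but it uses neither the preoperative side difference nor the order, and the role of Mann-Whitney is unexplained.

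On either reading, raw value or change could be chosen after the data are seen. A null result under reading (a) could reflect the test and not the materials. Chi-square for categorical outcomes is outside this point.

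**Working it through.** The documents give no SD, effect size or power, so there is no figure of the plan's own to reproduce. The size is illustrated under assumptions.

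**Inputs.** From the documents: 50 patients, both sides treated, 5% level (two-sided assumed). Assumed: swelling SD s = 3 mm, between-side correlation r = 0.5, true difference 1.5 mm, left-right asymmetry SD a = 0.5 to 2 mm per side, measurement-error SD e = 1 or 2 mm, facial-size SD F = 3, 6 or 9 mm, order 25:25.

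**1. Variance of the within-patient difference between sides**
- Raw day-2 value: 2s²(1−r) + 2a² + 2e² = 9 + 2a² + 2e².
- Change from preoperative: 9 + 4e² = 13 (e = 1) or 25 (e = 2).
- After regression on the preoperative side difference: 9 + 2a² + 2e² − 2a⁴/(a² + e²).

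Regression against raw value: 12/13 = 0.92 (a = 1, e = 1); 12.6/19 = 0.66 (a = 2, e = 1); 21/25 = 0.84 (a = 2, e = 2).

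**2. Reading (a), no true difference.** An unpaired test works as if the variance of the difference were the sum of the two side variances. For change this is 2(s² + 2e²) = 22 (e = 1) or 34 (e = 2), against true values of 13 and 25. By normal approximation:
- e = 1: √(13/22) = 0.77; 1.96/0.77 = 2.55; rejection about 1.1%. Simulation of Mann-Whitney itself gives 1.2%.
- e = 2: √(25/34) = 0.86; 1.96/0.86 = 2.29; rejection about 2.2%.
- Raw distances, F = 6: 0.0% in simulation.

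The paired tests reject in 4.7–5.5%.

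**3. Reading (a), power for 1.5 mm (4000 simulated trials per setting)**

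| Analysed value | Setting | Mann-Whitney | Signed-rank, side v side |
|---|---|---|---|
| Change | e = 1 | 60–62% | about 80% |
| Change | e = 2 | 39–42% | about 53% |
| Raw day 2 | F = 3 | 22–31% | 53–85% |
| Raw day 2 | F = 6 | 2–4% | 53–85% |
| Raw day 2 | F = 9 | below 1% | 53–85% |

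The paired results do not depend on F, because facial size cancels.

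**4. Reading (b), power: signed-rank on raw values v regression on baseline and order**

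| Asymmetry SD | e = 1 | e = 2 |
|---|---|---|
| 0.5 mm | 85 v 86% | 68 v 69% |
| 1 mm | 80 v 84% | 64 v 66% |
| 1.4 mm | 74 v 83% | 60 v 64% |
| 2 mm | 65 v 82% | 53 v 61% |

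Repeat simulations put the gain at about 0 to 19 points, and at −1 to +17 against a paired t-test. Mouth opening has no asymmetry and gains nothing: signed-rank 85–87% v regression 86–88% at e = 1.

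The undefined variable matters even when the test is paired. At a = 2, e = 1, signed-rank has 65% on raw values and about 80% on change. At a = 0.5, e = 2, it has 68% on raw values and about 53% on change.

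**5. Order.** The randomisation method is not stated. If it is simple, P(30:20 or worse) = 2 × P(X ≥ 30), X ~ Binomial(50, 0.5), = 0.20. An assumed order effect of 1.5 mm then shifts the unadjusted estimate by 1.5 × (30 − 20)/50 = 0.3 mm, to 1.8 or 1.2. Averaged over randomisation the shift is zero, and an order term removes it for the realised split.

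**6. Limit of baseline adjustment.** The second preoperative value is taken after the first material has been used. If a 1 mm differential residual enters that value only, the adjusted estimate is off by about 0.5 × slope, with slope = a²/(a² + e²): 0.03 mm at slope 0.06, 0.4 mm at slope 0.8. If it enters both preoperative and postoperative values, the unadjusted estimate is off by 0.5 mm and adjustment reduces the error.

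**The case against.** The strongest reply is that reading (b) is natural. The protocol uses the word group for the two sides of a patient, so dependent groups can mean side versus side. The comparison would then be valid, and the gain from baseline and order is only 1 to 4 points when asymmetry is 0.5 to 1 mm. The preoperative measurements are taken in order to assess edema and trismus, which points to change scores and not raw facial lengths. The unpaired test also errs on the conservative side.

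Much of this stands, and it rules out three stronger conclusions that a reader might draw:

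- **That the between-material test has almost no power.** This needs reading (a), raw distances and a large facial-size SD together. At 3 mm, power is 22–31%; on change scores it is 39–62%.
- **That the preoperative values are used nowhere.** A before-versus-after Wilcoxon would use them, though only within a material. The supportable statement concerns comparisons between materials.
- **That ignoring order biases the result, or that Mann-Whitney inflates false positives.** Order is randomised, so it does not bias in expectation, and with positively correlated sides the unpaired test rejects too rarely.

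The reply does not settle the text. Mann-Whitney, not Wilcoxon, is the test assigned to group means, and no sentence selects reading (b), change scores or a time point. The documents also give no reason to expect a residual effect on the opposite side, so the carry-over limit is a caution and not a prediction.

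**Conclusion.** The point holds as a defect of test choice and definition. On reading (a) the materials are compared by a test that ignores the pairing. Under the assumed values it rejects about 0–1% of the time under no difference with 1 mm measurement error (about 2% for change with 2 mm), and loses roughly 11 to 20 points of power on change scores. The loss is larger on raw distances and grows with facial-size SD. On reading (b) the test is valid and the cost is efficiency only: close to nothing when left-right asymmetry is small relative to measurement error, up to about 19 points when it is large. No baseline gain is claimed for mouth opening or pain.

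Every SD, correlation and effect is assumed, so the percentages show direction and rough size only. That the groups are paired, that the Wilcoxon pair is undefined, and that no between-material analysis mentions baseline or order comes from the text alone. The plan should be changed on this point; confidence in the size is moderate.

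**What to change.** In Statistical Data Analysis:

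1. State that every between-material comparison of continuous outcomes is within-patient and that an unpaired Mann-Whitney between sides is not used.
2. Name the analysed variable and time point for each outcome, and label any before-versus-after Wilcoxon as descriptive.
3. For facial distances and periodontal measures, take the difference between materials within each patient. Regress the postoperative difference on the preoperative difference plus an order term coded +1/2 or −1/2. Report the intercept with its 95% CI, and the unadjusted paired estimate beside it.
4. For pain, mouth opening and soft tissue opening, use the paired comparison with an order term.
5. For plaque index, use a paired rank test.

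Assigning order in balanced blocks (25:25) is optional.

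**Cost.** Wording only, with no new measurements, visits or patients. The regression spends two degrees of freedom, about 1 point of power against a paired t-test when asymmetry is small. It can introduce bias if the first material affects the second preoperative value, which is why the unadjusted paired estimate is kept.
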